1.3 Statistical Hypotheses for Trial Objectives

The primary hypothesis of this study is that Sirukumab in combination with SOC results in a statistically significant shorter time to sustained improvement (defined as a sustained improvement of at least 2 categories relative to baseline on the 6-point ordinal CRS) versus placebo in combination with SOC, in participants with confirmed critical COVID-19 disease.

1.4 Sample Size Justification

The study was targeted to enroll 270 participants with confirmed severe or critical COVID-19 disease in a 2:1 manner, with approximately 180 participants in the Sirukumab treatment arm and approximately 90 participants in the control arm. However, based on the rapidly evolving space of COVID-19 therapeutics focusing on the highly impacted population of critical patients together with the results from the interim analysis, the study population is being limited with protocol amendment 5 to a subset of the currently eligible population, ie, those with confirmed critical COVID-19 disease.

At the time of release of protocol amendment 5, approximately 100 participants with confirmed severe COVID-19 had been enrolled.

The study aims to enroll approximately 111 participants with confirmed critical COVID-19 disease overall in the study, with approximately 74 participants in the Sirukumab treatment arm and approximately 37 participants in the control arm.

The primary endpoint in this study is the time to sustained improvement of at least 2 categories relative to

Baseline on the 6-point ordinal clinical recovery scale, with participants who die prior to Day 28 treated as right censored at Day 28. For the sample size calculation on the primary endpoint, the following assumptions are used for survivors and participants who die prior to Day 28:

- For survivors in the control arm, it is assumed that the log transformed time to sustained improvement (days) follows a normal distribution with mean of log 28 and a standard deviation 0.9. Sirukumab is assumed to reduce the median time to sustained clinical improvement from 28 days to 16.8 days (40% reduction) in the surviving participants and is assumed to have the same standard deviation of 0.9.
- For the mortality rate in the control arm, 40% by Day 28 is assumed. Sirukumab is assumed to reduce the mortality with an absolute difference of 20%: from a mortality rate of 40% in the control arm to 20% (50% relative reduction).

Under these assumptions, at least 111 participants with confirmed critical COVID-19 disease are required to have at least 80% power to demonstrate a difference with the log-rank test, at a significance level of 5% two-sided.

The proportion of participants with a clinical improvement of at least 2 categories at Day 28 is a key secondary endpoint. Based on simulations using the above assumptions, the rate with clinical improvement at Day 28 in the control arm is expected to be 30%. The targeted treatment effect is an absolute increase of 25% (from 30% in the control arm to 55% in the Sirukumab arm) on this key secondary endpoint. The mortality by Day 28 is considered another key secondary endpoint. The targeted treatment effect is an absolute reduction in mortality by 25% (from 40% in the control arm to 15% in the Sirukumab arm). Under the aforementioned assumptions and with a sample size of 111, at least 80% power is obtained for both key secondary endpoints a 1-sided significance level of 5%.

1.5 Randomization and Blinding

Randomization

Central randomization will be implemented in this study. Participants will be randomly assigned to 1 of 2 treatment arms in a 2:1 ratio (Sirukumab: placebo) based on a computer-generated randomization schedule prepared before the study by or under the supervision of the sponsor. The randomization will be balanced by using randomly permuted blocks and will be stratified for age (<65 and \geq 65 years) and IMV (yes/no) at randomization. The interactive web response system (IWRS) will assign a unique intervention code, which will dictate the intervention assignment and matching study intervention kit for the participant assigned to the active study treatment. The requestor must use his or her own user identification and personal identification number when contacting the IWRS and will then give the relevant participant details to uniquely identify the participant.

Blinding

The investigator will not be provided with randomization codes. The codes will be maintained within the IWRS, which has the functionality to allow the investigator to break the blind for an individual participant.

Data that may potentially unblind the treatment assignment (ie, preparation) will be handled with special care to ensure that the integrity of the blind is maintained and the potential for bias is minimized.

The participants, study-site personnel, and investigators will be blinded to treatment allocation throughout the study, except for the designated pharmacist(s) or independent qualified staff member(s) with primary responsibility for study preparation. These unblinded members will not be part of the team performing the evaluations. The infusion administrator will be blinded and can perform other study evaluations. The sponsor study team will be blinded to study treatment allocation until the database release of the primary analysis.

Under normal circumstances, the blind should not be broken until the database for the primary analysis is locked. However, for the IA, the randomization codes and the translation of randomization codes into treatment and control groups were disclosed to those authorized and only for those participants included in the IA. Details on the level of unblinding and the parties authorized unblinded during the interim analysis were specified in the IA SAP. Otherwise, the blind should be broken only if specific emergency treatment/course of action would be dictated by knowing the treatment status of the participant. In such cases, the investigator may in an emergency determine the identity of the intervention by contacting the IWRS. While the responsibility to break the intervention code in emergency situations resides solely with the investigator, it is recommended that the investigator contact the sponsor or its designee if possible, to discuss the particular situation, before breaking the blind. Telephone contact with the sponsor or its designee will be available 24 hours per day, 7 days per week. In the event the blind is broken, the sponsor must be informed as soon as possible. The date and reason for the unblinding must be documented in IWRS, in the appropriate section of the eCRF and in the source document. The documentation received from the IWRS indicating the code break must be retained with the participant's source documents in a secure manner.

Participants who have had their intervention assignment unblinded should continue to return for scheduled evaluations.

In general, randomization codes will be disclosed fully only at the timing of the primary analysis and when the clinical database is closed. However, for the analyses performed for the DMC review or for the interim analysis, the randomization codes and, if required, the translation of randomization codes into intervention and control groups were disclosed to those authorized and only for those participants included in the DMC or interim analysis.

[figure not shown]
2 GENERAL ANALYSIS DEFINITIONS

All analysis dataset preparations and statistical analyses will be performed using SAS® version 9.4 or higher.

2.1 Visit Windows and Phase Definitions

The study is set up as shown in Figure 1 and Figure 2. The phases will be constructed as shown in Table 1.

Figure 1: Schematic Overview of the Study up to Protocol Amendment 4

COVID-19: coronavirus disease 2019; DMC: Data Monitoring Committee, EOT: end of trial, ICU: intensive care unit, IV: intravenous, PBO: placebo, SOC: standard of care

- * Randomization will be stratified by age (<65 and ≥65 years of age) and by use of invasive mechanical ventilation (yes/no) at the time of randomization.
- The DMC will review the interim data as soon as the first 30 participants have been dosed and have had at least 7 days of follow-up after study intervention.
- An IA for futility will be performed when approximately 20% of the planned number of participants have reached Day 28 or discontinued earlier.
- # Up to Day 28 or until hospital discharge or study discontinuation, whichever comes first. If a participant is discharged before Day 28, a phone call visit will be performed at Day 28.
- § SOC treatment (during study treatment and follow-phase) is determined by the investigator based on local practice and consists of supportive care.

SARS-CoV-2 PCR positivity at any time before screening will be accepted. Results from local laboratory, ECG^a, and pulmonary imaging assessments taken up to 2 days prior to screening will be accepted for screening assessments.

Screening^b assessments start after signing of the ICF and can continue on the next calendar day, if needed. All screening and baseline assessments may also take place on the same day.

^a As of protocol amendment 5

^b If the participant is on invasive mechanical ventilation or veno-venous ECMO, duration may not be >48 hours at time of screening.

[figure not shown]
Participants need to receive study intervention preferably within 4 hours but no later than 6 hours after randomization.

During the period covered up to and including protocol amendment 4:

- The DMC reviewed the interim data as soon as the first 30 participants with confirmed severe or critical COVID-19 disease had been dosed and had had at least 7 days of follow-up after study intervention.
- An IA for futility was performed when approximately 20% of the planned number of participants with confirmed severe or critical COVID-19 disease have reached Day 28 or discontinued earlier.

Figure 2: Schematic Overview of the Study as of Protocol Amendment 5

As of protocol amendment 5, participants with confirmed severe COVID-19 disease are no longer enrolled in the study and the study aims to enroll approximately 111 participants with critical COVID-19 overall in the study. At the time of release of protocol amendment 5, approximately 100 participants with confirmed severe COVID-19 disease had been enrolled.

2.1.1 Phase Definitions

Table 1: Construction of phases

| Study Phase | Start Date/Time | End Date/Time |
|---------------------|---|--|
| Screening (phase 1) | The date & time of signing the informed consent ^{*1} | 1 minute before the study drug intake |
| Treatment (phase 2) | Date & time of study drug administration (Sirukumab or Placebo) ^{*2} | Minimum of: a. Day 28 Visit at 23.59h or if Discharged earlier phone call Day 28 at 23.59h b. Date of study discontinuation before Day 28 ^{*3} c. Date of death ^{*3} If a), b) c) did not occur then count 28 days after drug administration at 23.59h |
| Follow-up (phase 3) | End of the treatment phase +1 minute | Maximum of: a. Date of last contact ^{*3} b. Date of study discontinuation ^{*3} |

^{*1}: if no time is available then impute with 00:00

^{*2}: in case the time part of the study drug administration is missing then time part will be imputed by time of randomization

^{*3}: Time will be imputed with 23:59

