1.3. Schedule of Activities (SoA)

Safety laboratory testing (hematology, chemistry, and coagulation tests) will routinely be performed by local laboratories (refer to Section 10.2 Appendix 2: Clinical Laboratory Tests and Section 10.3 Appendix 3: Clinical and Laboratory Assessments Described per Day).

	Screening Phase ^a	Phase Day 1 to Day 28			Post Day 28 Follow-up Phone Calls	
Day	Screening	Baseline ^a Day 1	Day 2 to Day 28 ^b or day of discharge from hospital ^{aa} , or study discontinuation, whichever comes first	Day 28 Visit if discharged earlier (Phone Call) Day 28 ±3 days	Day 56, Day 84, Day 112 ±7 days	
Week	Week 1	Week 1 (Day 2) to Week 4			Week 4	Week 8, 12, 16
General Screening/Baseline assessments						
ICF ^c	X					
Inclusion/exclusion criteria	X	X ^d				
Demographics, medical history ^c	X					
Targeted physical exam ^b	X		Any clinically significant findings to be reported			
Treatment administration						
Randomization ⁱ		X				
Administration of study intervention ⁱ		X				
Concomitant medication						
Concomitant medication recording	X	X	Throughout the study	X ⁿ	X ⁿ	
Respiratory function related assessments						
Type of supplemental oxygen	X	X	Once per day			
Resting SpO ₂ , FiO ₂ (if any) ^j	X	X	Minimum 4 times per day			
Arterial pH, PaO ₂ , PaCO ₂ ^j			As available			
Level of consciousness (Glasgow coma scale score) ^k	X	X	Once per day while in the ICU			
Pulmonary X-ray (or CT imaging or lung ultrasound if X-ray not available)	X ^{g,bb}		As per SOC, report upon worsening and last available			

	Screening Phase ^a	Phase Day 1 to Day 28				Post Day 28 Follow-up Phone Calls	
Day	Screening	Baseline ^a Day 1	Day 2 to Day 28 ^b or day of discharge from hospital ^{aa} , or study discontinuation, whichever comes first		Day 28 Visit if discharged earlier (Phone Call) Day 28 ±3 days	Day 56, Day 84, Day 112 ±7 days	
Week	Week 1		Week 1 (Day 2) to Week 4			Week 4	Week 8, 12, 16
General safety related assessments							
Standard 12-lead ECG	X ^{g,bb}		one ECG is to be taken between Day 4 and Day 8				
Vital signs (body temperature, pulse, SBP/DBP, respiratory rate)	X	X	As per SOC, minimum 4 times per day while in the ICU, afterwards once per day				
Any AE	X	X	Throughout the study				X ⁿ
Record discharge from ICU, discharge from hospital			As applicable				
Safety laboratory assessments^{dd}							
Hematology ^l	X ^g	X	Day 3, Day 7, Day 14, Day 21, Day 28 ^{cc}				
Chemistry ^l general safety	X ^g	X	Day 3, Day 7, Day 14, Day 21, Day 28 ^{cc}				

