Blood sample for SARS-CoV-2 viremia														X [•]
Nasopharyngeal swab for infections testing (PCR quantification of SARS-CoV-2 and multiplex PCR for detection of co-infections) ^{p,q}							X [•]							X ^{•,u,v}
If participants are intubated, an endotracheal sample for quantification of SARS-CoV-2 is to be taken in addition to the NP swab ^t							X [•]							X ^{•,u,v}
Stool sample (if feasible)							X [•]							X [•]
Biomarker/Pharmacology Assessments^{dd}														
CRP, Ferritin, D-dimer, Procalcitonin							X [•]							X [•]
Blood samples for cytokines, chemokines							X [•]							X [•]
Blood samples for various biomarkers														X [•]
Blood sample for SARS-CoV-2 specific antibodies														X [•]
Blood samples for pharmacology ^w							X [•]							X [•]
Blood samples for cellular profiling														X [•]

Day	Hospital Follow-Up (Day)													
	15	16	17	18	19	20	21	22	23	24	25	26	27	28 ^b
Week	3						4							
Exploratory Biomarkers/Pharmacogenomics^{dd}														
PAXgene blood for RNA profiling ^x														X [•]

- Laboratory testing to be performed centrally.

Note: If multiple assessments are scheduled for the same timepoint, it is recommended that procedures be performed in the following sequence: ECG, oxygen saturation, vital signs, blood sampling.

Hospitalization after Day 28, Discharge/Discontinuation Visit after Day 28, and Post-Hospitalization Follow-Up

	Hospital Follow-Up	Discharge / Discontinuation Visit		Post-hospitalization Follow-Up Phone Call			
Day	After Day 28 ^b (if hospitalized)	Discharge up to Day 28 ^{aa}	Discharge post Day 28 ^{aa}	Day 28 if discharged earlier (±3 days)	Day 56 (±7 days)	Day 84 (±7 days)	Day 112 (±7 days)
Week	Every Week (Once on the day of assessment unless specified differently below)			Week 4	Week 8	Week 12	Week 16
General Screening/Baseline assessments							
Targeted physical exam ^h	X	X	X				
	Any clinically significant findings to be reported						
Concomitant medication							
Concomitant medication recording	X	X	X	X ⁿ	X ⁿ	X ⁿ	X ⁿ
Respiratory function related assessments							
Type of supplemental oxygen	X	X	X				
Resting SpO ₂ , FiO ₂ (if any) ^j	X	X	X				
	Minimum 4x per day on the day of assessment						
Arterial pH, PaO ₂ , PaCO ₂ ^j	X	X	X				
	As available per day						
Level of consciousness (Glasgow coma scale score) ^k	X (if still in ICU)						
Pulmonary X-ray (or CT imaging or lung ultrasound if X-ray not available)	X	X	X				

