1.1 Trial Objectives

Primary Objective

The primary objective of the study is to evaluate the clinical response of Sirukumab (administered as a single IV dose) with standard-of-care (SOC) treatment compared to placebo with SOC in confirmed critical COVID-19 disease and as measured by the time to sustained improvement of at least 2 categories relative to baseline on the 6-point ordinal clinical recovery scale (CRS) (up to Day 28).

Secondary Objectives

| Objectives | Endpoints |
|---|---|
| Key Secondary | |
| To evaluate the clinical response of Sirukumab + SOC compared to placebo + SOC in confirmed critical COVID-19 disease | 
 Proportion of participants with an improvement on Day 28 of at least 2 categories relative to Baseline on the 6-point ordinal clinical recovery scale. Incidence of all-cause mortality (up to Day 28) |
| Other Secondary | |
| To evaluate the clinical response of Sirukumab+ SOC compared to placebo + SOC in confirmed severe or critical COVID-19 disease | 
 Time to sustained improvement of at least 2 categories relative to Baseline on the 6-point ordinal clinical recovery scale (up to Day 28) |
| To evaluate the clinical response of Sirukumab + SOC compared to placebo + SOC in confirmed severe or critical COVID-19 disease | 
 Proportion of participants with an improvement on Day 28 of at least 2 categories relative to Baseline on the 6-point ordinal clinical recovery scale Incidence of all-cause mortality (up to Day 28) |
| To evaluate the safety of Sirukumab + SOC compared to placebo + SOC | 
 Incidence of SAEs (up to Day 28) |

| | |
|--|---|
| in confirmed (a) critical and (b) severe or critical COVID-19 disease | 
 Incidence of related AEs (up to Day 28) Proportion of participants with severe or life-threatening bacterial, invasive fungal, viral or opportunistic infections (other than SARS-CoV-2) (up to Day 28) Incidence of grade 3 and 4 neutropenia and lymphocytopenia (up to Day 28) Incidence of increased ALT ≥ 3xULN combined with increased bilirubin > 2xULN (up to Day 28) |

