- Participants whose last score on the CRS was equal to 1 and that were not reported as having died before or at day 28 will be analyzed according to the composite strategy and they will be considered as alive (Death at Day 28=no).

Population level summary measure:

The difference in proportion of participants with ‘Death by day 28’ for experimental treatment versus placebo.

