6.5 Analysis of Undetectability of Viral Load

For the analysis of undetectability of viral load all subjects with at least a post-baseline measurement of viral load by Nasopharynx assay will be considered.

For the primary analysis, all measurements of viral load up to Day 31 of the study (i.e. protocol window: Day 28+3 days) by the NP assay from central lab (central lab) will be used. Plots for individual participants will be generated using data up to Week 16.

Time (Days) to undetectability of virus load will be evaluated using the **First confirmed undetectability (CU)** approach as described below.

First confirmed undetectability (CU)

A participant is said to have (CU) of viral load if (1) participant has two consecutive undetectable viral loads, or (2) if the last viral load in the database is undetectable.

If there is at least one incidence of the CU then the date of the first undetectability among all CUs will be used to find the days from the study dose date to first CU of viral load. If there is no CU until study Day 31 then participant will be censored at date of last viral load assessment until study Day 31.

Following rules will be applied to derive the flags for event (of first CU) or censoring, and to derive the Days to event or censoring.

[For clarity, in the examples below of different cases a detectable viral load is denoted by 'D', and undetectable by 'U', and 'x' will represent any type of load (undetectable or detectable)].

(1) Case when a participant has only 1 viral load measurement in database (therefore it is also the last viral load measurement):

- a. If the viral load is undetectable then censor flag = No (same as Event = Yes) [example: U => censor flag = No],

Days to event = date of last viral load measurement – dose date + 1.

- b. Otherwise if the viral load is detectable then censor flag = Yes (same as Event = No),
[example: D => censor flag = Yes].

Days to censoring = date of last viral load assessment – dose date + 1.

(2) Case when a participant has more than 1 viral load measurements in the database:

- a. if there are no cases of 'CU cases based on 2 consecutive viral loads' then
 - i. if last viral load in the database is undetectable then

censor flag = No (same as Event = Yes),
 [example: U₁DDU₂DU₃DU₄ => censor flag = No],

ii.if last viral load in the database is detectable then
 censor flag = Yes (same as Event = No),
 [example: U₁DDU₂DU₃D => censor flag = Yes],

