9.1.3 Analysis Methods

There will be no formal statistical testing for the AEs.

A summary table will be generated for the following attributes of AEs for 2 study phases (treatment phase, follow-up phase):

- any AE,
- serious AEs,
- AEs leading to death,
- AEs with grade ≥ 3 ,
- AEs with grade ≥ 3 and related to study drug,
- AEs related to study drug,
- AEs of special interest,
- AEs of special interest and related to study drug.

AE incidence tables will be generated showing the SOC-Med and PT separately in two phases (treatment and follow-up), in descending order of frequency in Sirukumab treatment arm. For each AE, the percentage of participants who experience at least 1 occurrence of the given event will be summarized. The tables will be provided for the following attributes:

- AEs by SOC-Med and PT,
- Serious AEs by SOC-Med and PT,
- AEs of special interest,
- AEs related to study drug,
- AEs with Grade ≥ 3 ,
- AEs leading to death.

Separate listings of participants with serious AE, AEs leading to death and AE ≥ 3 grade and AE related to study drug will be generated.

A table showing number of participants with SOC-Med of Infection and Infestation vs Lymphocytopenia Grade 3-4 during treatment phase will be generated.

Subgroup Analysis:

Tables for the following AE attributes will be generated by 2 subgroups: (Age: < 65 , ≥ 65 years, CRS score at baseline: ≤ 3 , ≤ 4 , 4, 5).

- Serious AEs,
- AEs of special interest, AEs related to study drug,
- AEs with Grade ≥ 3 ,
- AEs leading to death.

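### SAP Table 1 ends the treatment phase at the actual Day 28 contact, so AE and SAE endpoints defined to Day 28 can cover 25 to 31 days in participants discharged early

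*SAP*

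**What the plan says.** SAP 2.1.1 (Table 1) ends the treatment phase at the earliest of three dates: the Day 28 contact, study discontinuation before Day 28, or death. The contact is defined as "Day 28 Visit at 23.59h or if Discharged earlier phone call Day 28 at 23.59h". A fallback follows: "If a), b) c) did not occur then count 28 days after drug administration at 23.59h". Follow-up starts one minute after the treatment phase ends.

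The Schedule of Activities (Protocol 1.3) heads the relevant column "Day 28 Visit if discharged earlier (Phone Call) Day 28 ±3 days", and Protocol Appendix 3 repeats it as "Day 28 if discharged earlier (±3 days". Inpatients are assessed daily to Day 28, and only their laboratory sampling has a window (±1 day).

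The safety endpoints in SAP 1.1 run to Day 28, for example "Incidence of SAEs (up to Day 28". SAP 9.1.2 assigns each AE to a phase by its start date and time. SAP 9.1.3 then states: "AE incidence tables will be generated showing the SOC-Med and PT separately in two phases (treatment and follow-up". It specifies no table with a fixed Day 28 cut. SAP 1.1 also lists the incidence of SAEs to Week 16 as a secondary endpoint.

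**The concern.** Three different end dates sit behind one label: the Day 28 visit for inpatients, the call date for participants already discharged, and study Day 29 when neither contact took place. A discharged participant called on Day 25 has events from Days 26 to 28 moved into follow-up. One called on Day 31 has events from Days 29 to 31 counted as if they fell within Day 28.

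Only participants discharged early get the flexible end date, and time to discharge is something sirukumab is meant to change. The length of the safety window is therefore tied to a post-randomisation outcome, and the tables do not measure quite what the objectives define.

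A related gap concerns the Week 16 SAE endpoint. A participant with SAEs in both phases appears in both by-phase tables, so adding the tables does not give the proportion with any SAE from Day 1 to Week 16.

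**Working it through.** **Is the end date an actual contact or nominal Day 28?**
- The fallback applies when the listed events did not occur. A nominal date always occurs; a visit or call may not.
- SAP 6.5 uses measurements "up to Day 31 of the study (i.e. protocol window: Day 28+3 days", so the SAP itself recognises the contact window.
- The ICU-discharge rule in SAP 5.4.1 refers separately to the date of the Day 28 visit and to day 28.

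The actual-contact reading fits best.

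**Window length**
- Call window (Protocol 1.3 and Appendix 3): 28 − 3 = Day 25; 28 + 3 = Day 31. The upper end reproduces the SAP's own Day 31.
- Relative to 28 days: 25/28 − 1 = −10.7%; 31/28 − 1 = +10.7%. These are extremes for one participant.
- Fallback: Study Day 1 is the dosing day (SAP 2.3), so 28 days later is study day 1 + 28 = 29.

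**Effect on a measured risk.** Assume a constant hazard and a 28-day risk p. The documents give no AE risk, so a range is used. Then f(d) = 1 − (1 − p)^(d/28).

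| Assumed p | Day 25 | Day 28 | Day 31 |
|---|---|---|---|
| 10% | 9.0% | 10.0% | 11.0% |
| 20% | 18.1% | 20.0% | 21.9% |
| 30% | 27.3% | 30.0% | 32.6% |

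**Worst-case difference between arms with no true effect.** As a proxy for the share discharged, take the planned Day 28 improvement rates in SAP 1.4: 30% control and 55% sirukumab. Suppose every call is 3 days early, or every call is 3 days late.
- Difference in average window: (0.55 − 0.30) × 3 = 0.75 day; 0.75/28 = 2.7%.
- Spurious risk difference: (0.55 − 0.30) × [f(28 ± 3) − f(28)]. Computed on unrounded risks, early calls give −0.26, −0.48 and −0.68 percentage points for p = 10%, 20% and 30%. Late calls give +0.25, +0.47 and +0.66.
- If calls are symmetric around Day 28, the difference is essentially zero.

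**Vital status after an early call.** The next scheduled contact is Day 56 ± 7, that is Day 49 to 63. After a Day 25 call the gap is 49 − 25 = 24 to 63 − 25 = 38 days.

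No sample size, power or alpha figure depends on this point.

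**The case against.** The Table 1 wording can be read as nominal Day 28, and a footnote to the schema in SAP 2.1 places the call at Day 28. The fallback sentence argues against that reading. If nominal Day 28 was intended, the wording still needs correcting.

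The call window is two-sided and AEs are not formally tested (SAP 9.1.3). A reader might infer that the arms are observed for different lengths. The documents do not support that: it would need calls skewed in one direction as well as different discharge rates.

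A reader might also infer that Table 1 fixes Day 28 mortality early. It does not. Mortality is the worst CRS score at Day 28, taken from the date of death (SAP 5.2.1, 5.3.1), with days counted from dosing (SAP Attachment 3). Calls record the date of death, and Protocol 7.3 allows public sources to be searched. A death on Days 26 to 28 after a Day 25 call counts once it is reported. What remains is narrow. SAP 5.3.2 treats as alive "Participants whose last score on the CRS was equal to 1 and that were not reported as having died before or at day 28". An early call could therefore settle status at the primary analysis if the Week 8 call has not yet happened, or for good if the participant is later lost and no record is found.

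Nor are the laboratory endpoints (neutropenia, lymphocytopenia, ALT with bilirubin) materially affected. For participants discharged before Day 28, the last scheduled safety sample is at discharge.

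Finally, it would go too far to say that SAEs to Week 16 will never be counted. SAE listings are planned, and the table shells are in a separate document, the Data Presentation Specifications, which is not available here. What stands is that the SAP specifies no such count.

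**Conclusion.** The point holds for the AE, SAE, related-AE and severe-infection endpoints. As written, their window is 25 to 31 days for participants discharged early, 28 days for inpatients, and to study Day 29 under the fallback. This matters because the tables should match the stated endpoints; a large bias is not expected. The 0.3 to 0.7 percentage point bound rests on a constant hazard, assumed 28-day risks of 10% to 30%, discharge shares borrowed from the planned improvement rates, and every call being three days off in the same direction. The primary efficacy analysis does not use the treatment-phase end date. The missing once-per-participant count of SAEs to Week 16 is a separate, simple gap in the specification.

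**What to change.** All changes are to the SAP:

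- **2.1.1, Table 1:** end the treatment phase at study Day 28, 23:59, for everyone, or at earlier death or discontinuation, whatever the call date. Alternatively, keep the phases and cut the AE and SAE endpoints defined to Day 28 at that time by onset date. Set the fallback to study Day 28 as well.
- **9.1.3:** add SAE incidence from Day 1 to Week 16, counting each participant once.
- **Vital status:** for participants whose call fell before Day 28, confirm status on or after Day 28 before the primary database lock where possible.

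The cost is a few lines of text, one derived date, one table column and a small number of site queries. The call window in the Schedule of Activities can stay. Changing it would need a protocol amendment and is unnecessary, because events on Days 26 to 28 reported at a later call are placed correctly by onset date. Some may reach the database only after the primary analysis; the final analysis would include them.
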